**Table 11-1 Criteria for Potentially Clinically Significant Laboratory Tests**

Parameter	SI Unit	Lower Limit	Higher Limit
CHEMISTRY			
Albumin	g/L	< 0.9 * LLN	> 1.1 * ULN
Alanine Aminotransferase (ALT)	U/L	—	≥ 3 * ULN
Alkaline Phosphatase	U/L	—	≥ 3 * ULN
Aspartate Aminotransferase (AST)	U/L	—	≥ 3 * ULN
Calcium	mmol/L	< 0.9 * LLN	> 1.1 * ULN
Chloride	mmol/L	< 0.9 * LLN	> 1.1 * ULN
Cholesterol	mmol/L	—	> 1.6 * ULN
Creatinine	µmol/L	—	> 1.3 * ULN
Potassium	mmol/L	< 0.9 * LLN	> 2.0 * ULN
Glucose, Fasting	mmol/L	< 0.9 * LLN	> 1.4 * ULN
Sodium	mmol/L	< 0.9 * LLN	> 1.1 * ULN
Total Bilirubin	µmol/L	—	> 1.5 * ULN
Total Protein	g/L	< 0.9 * LLN	> 1.1 * ULN
Triglycerides, Fasting	mmol/L	—	≥ 3 * ULN
Urea (BUN)	mmol/L	—	> 1.2 * ULN
Magnesium	mmol/L	< 0.9 * LLN	> 1.1 * ULN
Bicarbonate	mmol/L	< 0.9 * LLN	> 1.1 * ULN
Phosphate	mmol/L	< 0.9 * LLN	> 1.1 * ULN
Uric Acid	µmol/L	< 0.9 * LLN	> 1.1 * ULN
HEMATOLOGY			
Basophils Absolute Cell Count	10  /L	—	> 3 * ULN
Eosinophils Absolute Cell Count	10  /L	—	> 3 * ULN
Hematocrit	Ratio	< 0.9 * LLN	> 1.1 * ULN
Hemoglobin	g/L	< 0.9 * LLN	> 1.1 * ULN
Lymphocytes Absolute Cell Count	10  /L	< 0.8 * LLN	> 1.5 * ULN
MCH	PG	—	> 3 * ULN
MCHC	G/L	—	> 3 * ULN
MCV	fL	< 0.9 * LLN	> 1.1 * ULN
Monocytes Absolute Cell Count	10  /L	—	> 3 * ULN
Neutrophils Absolute Cell Count	10  /L	< 0.8 * LLN	> 1.5 * ULN
Platelet Count	10  /L	< 0.5 * LLN	> 1.5 * ULN
Red Blood Cell Count (Erythrocyte Count)	10  /L	< 0.9 * LLN	> 1.1 * ULN
White Blood Cell Count	10  /L	< 0.7 * LLN	> 1.5 * ULN
URINALYSIS			
pH		< 0.9 * LLN	> 1.1 * ULN
Specific Gravity		—	> 1.1 * ULN

LLN: Lower limit of normal value provided by the laboratory.

ULN: Upper limit of normal value provided by the laboratory.

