Clinical laboratory test values will be considered potentially clinically significant (PCS) if they meet either the lower-limit or higher-limit PCS criteria listed in [Table 11-1](#). The number and percentage of participants who have PCS post-baseline clinical laboratory values will be tabulated by study intervention at each assessment. The percentages will be calculated relative to the number of participants who have available non-PCS baseline values and at least 1 post-baseline assessment. The numerator will be the total number of participants with at least 1 PCS post-baseline value. A supportive listing of participants with PCS post-baseline values will be provided for the Safety and Safety-T3 Populations.

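### SAP Table 11-1 sets upper PCS limits for potassium, MCH, MCHC and urine specific gravity that are practically unattainable, so the PCS counts and PCS listing cannot detect elevations in these four parameters

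*SAP*

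**What the plan says.** Protocol Section 9.4.2.2 leaves the PCS laboratory criteria to the SAP, so Table 11-1 is where they are set. Under SAP Section 11.2 a value is PCS "if they meet either the lower-limit or higher-limit PCS criteria listed in" that table. The use made of the flag is also stated there: "The number and percentage of participants who have PCS post-baseline clinical laboratory values will be tabulated by study intervention at each assessment". On counting, it adds: "The numerator will be the total number of participants with at least 1 PCS post-baseline value". A supportive PCS listing follows from the same flags.

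The rows at issue in Table 11-1 are:

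- Potassium: "Potassium mmol/L < 0.9 * LLN > 2.0 * ULN".
- Sodium, for comparison: "Sodium mmol/L < 0.9 * LLN > 1.1 * ULN". Chloride and calcium carry the same pair of multiples, and so do magnesium ("Magnesium mmol/L < 0.9 * LLN > 1.1 * ULN"), bicarbonate and phosphate.
- MCH and MCHC: an upper limit of 3 * ULN and no lower limit. MCV, another red-cell index in the same table, has 0.9 * LLN and 1.1 * ULN.
- Urine specific gravity: "Specific Gravity — > 1.1 * ULN".

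The table footnote gives the source of the limits ("ULN: Upper limit of normal value provided by the laboratory"), but no numerical ULN appears in either document.

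**The concern.** The potassium row is lopsided without any assumption about the ULN. Its lower limit follows the pattern of the other electrolytes; its upper limit does not, and no reason is given. Eleven chemistry rows have a lower limit of 0.9 * LLN. Nine of them pair it with 1.1 * ULN: albumin, calcium, chloride, sodium, total protein, magnesium, bicarbonate, phosphate and uric acid. Glucose uses 1.4. Potassium alone uses 2.0.

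A PCS table is meant to let a reader compare how many participants in each arm crossed a stated threshold. If the threshold cannot in practice be crossed, the comparison carries no information. A reader who sees no high-potassium flags in either arm may nevertheless take it as evidence of safety. The same applies to MCH, MCHC and specific gravity.

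**Working it through.** The plan states multipliers and derives no figure from them, so there is nothing of its own to reproduce. The check is multiplier times ULN, over a range of assumed ULNs.

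**Inputs.** The multipliers are from SAP Table 11-1. The ULNs are assumptions: potassium 5.0 to 5.5 mmol/L, MCH 32 to 34 pg, MCHC 350 to 370 g/L, specific gravity 1.025 to 1.035.

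**Cut-off = multiplier × ULN**

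| Parameter | As written | With 1.1 * ULN |
|---|---|---|
| Potassium (mmol/L) | 2.0 × 5.0 = 10.0 to 2.0 × 5.5 = 11.0 | 1.1 × 5.0 = 5.5 to 1.1 × 5.5 = 6.05 |
| MCH (pg) | 3 × 32 = 96 to 3 × 34 = 102 | 1.1 × 32 = 35.2 to 1.1 × 34 = 37.4 |
| MCHC (g/L) | 3 × 350 = 1050 to 3 × 370 = 1110 | 1.1 × 350 = 385 to 1.1 × 370 = 407 |
| Specific gravity | 1.1 × 1.025 = 1.1275 to 1.1 × 1.035 = 1.1385 | already 1.1 |

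**Scale check for potassium.** Treat the reference range as mean ± 1.96 SD, so SD = (ULN − LLN)/3.92, with an assumed LLN of 3.5 mmol/L.

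- Range 3.5 to 5.0: midpoint 4.25, SD = 1.5/3.92 = 0.383. The written upper cut-off lies (10.0 − 4.25)/0.383 ≈ 15.0 SD above the midpoint. At 1.1 * ULN it would lie (5.5 − 4.25)/0.383 ≈ 3.3 SD above. The existing lower cut-off, 0.9 × 3.5 = 3.15, lies (4.25 − 3.15)/0.383 ≈ 2.9 SD below.
- Range 3.5 to 5.5: midpoint 4.5, SD = 2.0/3.92 = 0.510. The corresponding distances are (11.0 − 4.5)/0.510 ≈ 12.7 SD above, (6.05 − 4.5)/0.510 ≈ 3.0 SD above, and (4.5 − 3.15)/0.510 ≈ 2.6 SD below.

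The lower flag and a 1.1 upper flag would sit at similar distances from mid-range. The written upper flag sits four to five times as far out (12.7/3.0 ≈ 4.2; 15.0/3.3 ≈ 4.5).

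**Why specific gravity fails with the multiple used elsewhere.** The scale starts near 1, so a 10% increase in the number is a very large increase in what it measures. The excess over 1 would have to rise from 0.025 to 0.1275 (5.1 times) or from 0.035 to 0.1385 (4.0 times).

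**Rows not included.** Most other upper limits are attainable. Sodium, for example, is flagged above 1.1 × 145 = 159.5 to 1.1 × 147 = 161.7 mmol/L (ULN 145 to 147 assumed). Urine pH depends on the ULN: 8.0 gives 8.8, above the highest coded example of 8.5 in SAP Table 16-1, but 7.5 gives 8.25, which can be reached.

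**The case against.** A reader might infer that hyperkalaemia would be reported as zero events whatever happens. The documents do not support that. Four routes do not pass through Table 11-1:

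- Protocol Section 8.2.4 has investigators record clinically relevant laboratory changes as adverse events, and Protocol Appendix 3 counts clinically significant abnormal results as such.
- SAP Section 11.1 tabulates treatment-emergent adverse events by preferred term, severity and arm.
- SAP Section 11.2 summarises values and changes from baseline by arm, and Section 11.0 includes the maximum among the summary statistics.
- SAP Section 16.3 puts all assessments in the data listings.

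Nor is Table 11-1 the only count of laboratory abnormalities, since SAP Section 11.5.2 summarises potential Hy's Law cases. All this stands, but none of these routes gives what the PCS table is for. A maximum does not say how many participants were high, adverse event recording rests on investigator judgement, and listings give no percentage by arm.

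A second inference, that the tables will show a high-potassium row at 0% in each arm, also goes too far. Section 11.2 does not say that high and low flags are tabulated separately, and table layouts are in a separate document (SAP Section 4.0). If they are pooled, the potassium row may be non-zero, but in practice only through low values. Even an upper count of zero is a practical expectation and not a logical certainty, because an artefactual result could exceed 10 mmol/L.

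Other objections carry some weight. Magnesium, bicarbonate and phosphate are not in the chemistry panel listed in Section 11.2, so the measured comparators are sodium, chloride and calcium; all three use 1.1. Multiples differ elsewhere in the table, so a different one is not an error in itself; the fault is that this one cannot work. MCH and MCHC are ratios of hemoglobin, red cell count and hematocrit, which are flagged at 0.9 and 1.1, so less is lost there. The documents name no potassium risk; the only adverse event of special interest is hypersensitivity.

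**Conclusion.** The point holds for the PCS counts and the PCS listing, and for four parameters: potassium, MCH, MCHC and urine specific gravity. Their upper limits are practically unattainable, so these outputs cannot detect elevations. For potassium, values between 1.1 and 2.0 times ULN (5.5 to 10.0 mmol/L at a ULN of 5.0; 6.05 to 11.0 at 5.5) would be flagged under the other electrolytes' multiple and are not flagged as written.

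The mmol/L, pg, g/L and specific gravity figures all rest on assumed ULNs, and the SD distances also on an assumed LLN and a normal reference range. No ULN in the ranges tried changes the conclusion. The mismatch between potassium's upper limit, its own lower limit and the other electrolytes needs no assumption. The primary analysis and the type I error are untouched. This is a correction to a safety output that should be made, not a threat to the trial's main conclusion.

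**What to change.** Amend SAP Table 11-1 before database lock and unblinding:

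- Potassium, higher limit: > 1.1 * ULN, the table's own multiple for electrolytes, or keep 2.0 with a stated justification.
- MCH and MCHC, higher limit: > 1.1 * ULN, as for MCV.
- Urine specific gravity: replace the multiple with an attainable criterion, or delete the row.

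These are analysis flags and do not alter how any participant is managed. It would help to state in Section 11.2 whether high and low flags are tabulated separately, so that a reader can tell what a potassium count means.

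The cost is a table edit and reprogramming of the flags, with no new data. Some PCS counts will rise. Denominators may fall slightly, because percentages are based on participants with a non-PCS baseline value and a few may now be PCS at baseline.

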### 11.3 VITAL SIGNS

Descriptive statistics for vital signs (systolic and diastolic BP, pulse rate, weight, respiration rate, and temperature) at baseline (screening) and changes from baseline at each assessment will be presented by study intervention.

Vital sign values will be considered PCS if they meet both the observed-value criteria and the change from baseline criteria listed in [Table 11-2](#). The number and percentage of participants who have PCS post-baseline clinical laboratory values will be tabulated by study intervention at each assessment. The percentages will be calculated relative to the number of participants who have available non-PCS baseline values and at least 1 post-baseline assessment. The numerator will be the total number of participants with at least 1 PCS post-baseline value. A supportive listing of participants with PCS post-baseline values will be provided for the Safety and Safety-T3 Populations.

**Table 11-2 Criteria for Potentially Clinically Significant Vital Signs**

Parameter	Flag	Criteriaa	
		Observed Value	Change From Baseline
Sitting systolic blood pressure, mm Hg	High	≥ 140	Increase of ≥ 20
	Low	≤ 90	Decrease of ≥ 20
Sitting diastolic blood pressure, mm Hg	High	≥ 90	Increase of ≥ 15
	Low	≤ 50	Decrease of ≥ 15
Sitting pulse rate, bpm	High	≥ 100	Increase of ≥ 15
	Low	≤ 50	Decrease of ≥ 15
Weight, kg	High	—	Increase of ≥ 7%
	Low	—	Decrease of ≥ 7%

a A post-baseline value is considered potentially clinically significant if it meets both the observed-value and the change from baseline criteria.

bpm = beats per minute.

### 11.4 ELECTROCARDIOGRAM

Descriptive statistics for ECG parameters (heart rate, PR interval, QRS duration, QT interval, and QTc) at baseline, EOS, changes from baseline at EOS, interim ECG parameters at baseline (pre-dose at each period), and changes from baseline at post-dose will be presented by study intervention.

Electrocardiographic parameter values are considered PCS if they meet or exceed the higher-limit PCS criteria listed in [Table 11-3](#). The number and percentage of participants who have PCS post-baseline ECG values will be tabulated by study intervention for EOS assessments and interim assessments. The percentages will be calculated relative to the number of participants who have available non-PCS baseline values and at least 1 post-baseline assessment. The numerator will be the total number of participants with at least 1 PCS post-baseline value. A supportive listing of participants with PCS post-baseline values will be provided, including the participant number and baseline and post-baseline values, for the Safety and Safety-T3 Populations.

**Table 11-3** **Criteria for Potentially Clinically Significant Electrocardiographic Values**

Parameter	Unit	Criterion Value a	Change from Baseline a
QRS duration	msec	$\geq 150$	—
PR interval	msec	$\geq 250$	—
QTcF interval for male	msec	$> 450$	Increase of $> 60$
QTcF interval for female	msec	$> 470$	Increase of $> 60$

a post-baseline (end-of-study or post-dose) value will be considered potentially clinically significant if it meets the criterion value or the change from baseline or pre-dose value.

PCS = potentially clinically significant;

QTcF = QT interval/(60/RR)1/3.

## 11.5 OTHER SAFETY PARAMETERS

### 11.5.1 Physical Examination

Any new physical examination abnormality identified on the post-baseline physical examination or any physical examination abnormality noted as worsened from Screening (Visit 1) to the post-baseline physical examination will be reported as an AE if considered by the investigator to be clinically significant. No separate data analysis for physical exams is planned.

### 11.5.2 Potential Hy's Law

*Potential* Hy's Law criteria within a 24-hour window is defined by a post baseline elevation of alanine aminotransferase (ALT) or aspartate aminotransferase (AST)  $\geq 3x$  ULN, along with total bilirubin (TBL)  $\geq 2x$  ULN and a non-elevated alkaline phosphatase (ALP)  $< 2x$  ULN, all based on blood draws collected within a 24-hour period.

*Potential* Hy's Law criteria without time window (e-DISH) is defined by maximum of post baseline elevation of ALT or AST  $\geq 3x$  ULN, along with maximum of post baseline elevation of TBL  $\geq 2x$  ULN and a non-elevated alkaline phosphatase (ALP)  $< 2x$  ULN.

Participants who meet the potential Hy's Law criteria from the first dose of study drug to within 35 days after the last dose of study treatment will be summarized. Supportive tabular displays will also be provided.

**12.0**

**HEALTH OUTCOMES ANALYSES**

Analyses for health economics and outcomes parameters will be described in a separate document.

**13.0**

**INTERIM ANALYSIS**

No interim analysis is planned for this study.

14.0

## **DETERMINATION OF SAMPLE SIZE**

**15.0**

**STATISTICAL SOFTWARE**

Statistical analyses will be performed using version 9.4 (or newer) of SAS on a Linux operating system.

## **16.0**

## **DATA HANDLING CONVENTIONS**

### **16.1**

### **BASELINE DEFINITION**

Unless otherwise specified, the baseline value will be the last non-missing value obtained prior to or on the first treatment dose.

### **16.2**

### **VISIT TIME WINDOWS**

The following tables present the visits assigned for analyses and the corresponding range of treatment days (window) during which an actual visit may occur.

#### 1) Participants for 18-week Titration Period Visit Time Windows for Analysis

Derived Visit		Window
Visit 2 Baseline	Day 1	Days $\leq$ 1
Visit 3a Week 6	Day 42	Days [2, 63]
Visit 4a Week 12	Day 84	Days [64, 105]
Visit 5a Week 18	Day 126	Days [106, last day of TP]
Visit 6 Week 24	Day 168	Days [first day of SP, 189]
Visit 7 Week 30	Day 210	Days $>$ 189

#### 2) Participants for 24-week Titration Period Visit Time Windows for Analysis

Derived Visit		Window
Visit 2 Baseline	Day 1	Days $\leq$ 1
Visit 3a Week 6	Day 42	Days [2, 63]
Visit 4a Week 12	Day 84	Days [64, 105]
Visit 5a Week 18	Day 126	Days [106, 147]
Visit 5c Week 24	Day 168	Days [148, last day of TP]
Visit 6 Week 30	Day 210	Days [first day of SP, 231]
Visit 7 Week 36	Day 252	Days $>$ 231

3) Participants for 30-week Titration Period Visit Time Windows for Analysis

Derived Visit		Window
Visit 2 Baseline	Day 1	Days $\leq$ 1
Visit 3a Week 6	Day 42	Days [2, 63]
Visit 4a Week 12	Day 84	Days [64, 105]
Visit 5a Week 18	Day 126	Days [106, 147]
Visit 5c Week 24	Day 168	Days [148, 189]
Visit 5e Week 30	Day 210	Days [190, last day of TP]
Visit 6 Week 36	Day 252	Days [first day of SP, 273]
Visit 7 Week 42	Day 294	Days $>$ 273

4) Participants for 36-week Titration Period Visit Time Windows for Analysis

Derived Visit		Window
Visit 2 Baseline	Day 1	Days $\leq$ 1
Visit 3a Week 6	Day 42	Days [2, 63]
Visit 4a Week 12	Day 84	Days [64, 105]
Visit 5a Week 18	Day 126	Days [106, 147]
Visit 5c Week 24	Day 168	Days [148, 189]
Visit 5e Week 30	Day 210	Days [190, 231]
Visit 5g Week 36	Day 252	Days [232, last day of TP]
Visit 6 Week 42	Day 294	Days [first day of SP, 315]
Visit 7 Week 48	Day 336	Days $>$ 315

TP = Titration Period; SP = Stabilization Period.

Last day of TP is the day of last TSH visit prior to visit 6.

First day of SP is defined as the last day of TP + 1.

If the visit date is on or after the date of the first dose of double-blind study treatment, the study day is calculated by visit date – date of the first dose of double-blind investigational product + 1. If the visit date is before the date of the first dose of double-blind investigational product, the study day is calculated by visit date – date of the first dose of double-blind investigational product. Therefore, a negative day indicates a day before the start of the double blind investigational product.

If a participant has 2 or more visits within the same window, the last visit with a non-missing value will be used for analysis.

The titration visits 5b, 5d, and 5f will be included in the analysis visits 5a, 5c, 5e, or 5g based on the definition of analysis visit window.

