- Participants who need dose titration beyond Week 18 will complete a study visit approximately every 6 weeks to determine if their TSH levels are within the normal reference range. At these visits, they will have the same assessments performed as those performed at Visit 5a including study intervention dispensing. These assessment visits will be labeled sequentially 5c (Week 24), 5e (Week 30), and 5g (Week 36), as needed.
- Participants who need dose titration beyond Week 18 will also complete a study visit for additional study intervention dispensing. These study intervention visits will be labeled sequentially as 5b (Week 19), 5d (Week 25), and 5f (Week 31), as needed. Visit 5d and 5f will have all the same assessments and activities performed as Visit 5b.

The Titration Period is at least 18 weeks in duration. Depending on whether a participant requires additional dose titration after Visit 5a, the Titration Period may end at Week 18, 24, 30, or 36 (up to a maximum of 3 additional titrations are allowed starting at Visit 5b).

The Stabilization Period is 12 weeks in duration. Depending on whether a participant requires additional dose titration after Visit 5a, the Stabilization Period may end at Week 30, 36, 42, or 48. If a participant undergoes the maximum of 3 additional dose titrations starting at Week 5b, the Stabilization Period would be from Week 36 to Week 48.

Visit 6 may be at Week 24, 30, 36, or 42 depending on the number of additional titrations needed after Visit 5a. Visit 7 may be at Week 30, 36, 42, or 48 depending on the number of additional titrations needed after Visit 5a.

**Table 4-1** Schedule Activities

3014-201-002 Schedule of Activities											
	Screening	Titration Period (Week 0 to Week 18 a )							Stabilization Period (Week 18 a to Week 30 c )		Early Termination
		Visit 1	Visit 2	Visit 3a	Visit 3b d	Visit 4a	Visit 4b d	Visit 5a e	Visit 5b d,e	Visit 6 f	Visit 7 g
Visit Number	Visit 1										
Study Week	-3 to 0	0	6	7	12	13	18 d	19	24	30	
Visit Window	---	±3 days	±3 days	±3 days	±3 days	±3 days	±3 days	±3 days	±3 days	±3 days	
Informed consent	X										
Randomization		X									
Inclusion/exclusion	X	X									
Demographic data	X										
Medical history	X										
AEs	X	X	X	X	X	X	X	X	X	X	X
Clinical laboratory b,h,n	X	X	X		X		X		X	X	X
Vital signs b,i	X	X	X	X	X	X	X	X	X	X	X

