$$P_h = \left( n_{h1.}^2 \cdot n_{h21} - n_{h2.}^2 \cdot n_{h11} + n_{h1.} \cdot n_{h2.} \cdot (n_{h21} - n_{h11}) / 2 \right) / n_h^2$$

$$Q_h = (n_{h11}(n_{h2.} - n_{h21}) + n_{h21}(n_{h1.} - n_{h11})) / 2n_h$$

The  $100(1 - \alpha)\%$  confidence limits for the stratified proportion difference are

$$\hat{d}_{MH} \pm (z_{\alpha/2} \times \hat{\sigma}(\hat{d}_{MH}))$$

[REDACTED]

[REDACTED]

[REDACTED]

The **Non-Responder Imputation** incorporating multiple imputation to handle missing data due to **Covid-19 (NRI-C)** will be performed for participants who have missing TSH values either at the end of the Titration Period or at the end of the Stabilization Period. The NRI-C will categorize any participant who does not have an evaluation at the end of Titration Period or at the end of Stabilization Period as a non-responder. The only exception is that missing data solely due to COVID-19 infection or logistical restrictions related to the COVID-19 pandemic will be handled by Multiple Imputation (MI) under the Missing at Random (MAR) mechanism.

The analysis using NRI-C will be carried out in the following steps.

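### SAP 16.2 counts the Visit 6/Visit 7 cut-off from first dose, so if titration ends 22 or more days late a 6-week TSH can stand in for the end-of-Stabilization result

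*SAP*

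**What the plan says.** SAP 16.2 assigns visits to analysis windows by study day. For visits on or after first dose, "the study day is calculated by visit date – date of the first dose of double-blind investigational product + 1". There are four tables, for titration periods of 18, 24, 30 and 36 weeks.

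The end of titration is not capped in any of them. In the 18-week table the Visit 5a window is "Days [106, last day of TP"], and the notes add "Last day of TP is the day of last TSH visit prior to visit 6". Stabilization follows directly: "First day of SP is defined as the last day of TP + 1".

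The Visit 6 window has a floating start and a fixed end, for example "Days [first day of SP, 189"] in the 18-week table and "Days [first day of SP, 231"] in the 24-week table. Everything later is Visit 7. When several visits share a window, the latest one with a value is used.

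SAP 4.1 says "The Stabilization Period is 12 weeks in duration" and places Visit 6 six weeks, and Visit 7 twelve weeks, after the end of titration.

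For the primary analysis, SAP 10.1 counts a missing evaluation at either time point as non-response ("The NRI-C will categorize any participant who does not have an evaluation at the end of Titration Period or at the end of Stabilization Period"). A value missing only because of COVID-19 is excepted and multiply imputed.

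**The concern.** Two clocks run inside one window. The start of Stabilization moves with the participant, while the line between its 6-week and 12-week visits stays tied to first dose. When titration ends late, both Stabilization visits shift later and the line does not. No minimum time in Stabilization is required before a value counts as Visit 7.

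The primary endpoint is exposed when Visit 6 crosses the line and no later TSH exists. The participant is then scored on 6 weeks of fixed dosing as though 12 weeks had been observed, and the missing-data rule is never triggered. The non-responder, responder, multiple-imputation and tipping-point sensitivity analyses also act on missing TSH values, so they would not pick the case up. The complete-case analysis would drop the participant only if recorded as not having completed the study.

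If Visit 7 is attended, it is the later value and is selected, so the primary result stands. Visit 6 then disappears from by-visit summaries.

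**Working it through.** **Inputs (SAP 16.2 tables, in study days) and reproduction of the cut-offs.** Each stated cut-off is the midpoint of the nominal Visit 6 and Visit 7 days.

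| Table | Titration ends (T) | Visit 6 | Visit 7 | Cut-off (C) | Midpoint check | Slack after Visit 6 | C − T |
|---|---|---|---|---|---|---|---|
| 18-week | 126 | 168 | 210 | 189 | (168+210)/2 = 189 | 189−168 = 21 | 63 |
| 24-week | 168 | 210 | 252 | 231 | (210+252)/2 = 231 | 231−210 = 21 | 63 |
| 30-week | 210 | 252 | 294 | 273 | (252+294)/2 = 273 | 273−252 = 21 | 63 |
| 36-week | 252 | 294 | 336 | 315 | (294+336)/2 = 315 | 315−294 = 21 | 63 |

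**Delay at which Visit 6 is misfiled.** Let titration end L days late and Visit 6 be held 42 days after that. Visit 6 is filed as Visit 7 when T + L + 42 > C, that is, when L > 63 − 42 = 21.

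- L = 21: Visit 6 falls on Day 189/231/273/315, exactly on the cut-off, and is still Visit 6.
- L = 22: titration ends on Day 148/190/232/274 and Visit 6 falls on Day 190/232/274/316, which is filed as Visit 7 in all four tables.
- With Visit 6 itself 3 days late or 3 days early, the threshold is 19 or 25 days.
- Counting lateness from exactly 18/24/30/36 weeks after first dose (Day 127/169/211/253), it is 21 days.
- L = 63 or more: Stabilization starts after the cut-off and the Visit 6 window is empty.

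**Can permitted visit tolerance get there?** Suppose every 6-weekly TSH visit up to and including Visit 6 runs 3 days later than due from the one before. There are 4, 5, 6 or 7 such steps, giving Visit 6 on Day 168+12 = 180, 210+15 = 225, 252+18 = 270 and 294+21 = 315. None passes its cut-off, so the problem needs out-of-window visits.

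**Dependence on table assignment.** Under grouping by number of extra titrations, the results above apply to all four tables. Under grouping by actual duration, titration ending on Day 148 would move to the 24-week table, whose Visit 5c window starts on Day 148. Visit 6 on Day 190 would then fall before Day 231 and be filed correctly. The same rescue works for the 24-week table (Day 190, where the Visit 5e window starts) and the 30-week table (Day 232, where the Visit 5g window starts). The 36-week table has no later table to move to.

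**Size per participant.** With about 142 per arm (SAP 4.1), one participant switched from non-responder to responder moves that arm's rate by 1/142 = 0.70 points. Protocol 9.4.1.2 gives a margin of 10 points.

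**The case against.** The strongest objection is reachability. A 22-day delay is about seven times the ±3-day tolerance, and tolerance alone never produces it. That stands, and it is why the point is minor. The SAP's COVID-19 text covers enrolment, missing data and treatment discontinuation, and does not mention late visits. Pandemic delay is therefore a plausible inference that the plan does not state.

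Second, the endpoint link is inferred. SAP 10.1 refers to the end of Stabilization, not to derived Visit 7, and the protocol's section on primary-endpoint timing is not visible. The weeks given for the two in SAP 4.1 do match, which makes this the natural reading. The calculation also assumes that Visit 6 is booked 42 days after the actual end of titration; a Visit 6 held at its original study week would not cross the line.

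Third, other provisions narrow the affected group. TSH is scheduled at Early Termination (SAP Table 4-1), and such a value would displace Visit 6. SAP Appendix B assigns non-response after discontinuation of study drug unrelated to COVID-19. However, it also says data after the event are used, and it does not reach someone who stays on drug and misses Visit 7.

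A reader might also infer three stronger points that the documents do not support:

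- **Ordinary titration creates the drift**, because a changed dose is dispensed a week after the check. SAP 4.1 sets the later dispensing visits at Weeks 19, 25 and 31 and the checks at Weeks 24, 30 and 36, so each check comes five weeks after dispensing and nothing accumulates.
- **The misfiling favours one arm.** Extra titrations after Visit 5a move a participant to a table with a later cut-off; they do not use up the 21 days. Nothing shows that lateness differs by arm.
- **A certain number of participants will be affected.** The documents give no rate for late titration or for a missed Visit 7.

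**Conclusion.** The defect is real but narrow. As written, the rule can put a 6-week TSH in the 12-week slot and bypass the primary missing-data rule. It needs titration to end 22 or more days late, Visit 6 about 42 days after that, and no later TSH. It reaches all four tables or, clearly, only the 36-week table, depending on an assignment rule that the visible SAP does not give.

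The 0.70 points per participant is an upper limit. It applies only if the Visit 6 TSH is in range, the end-of-titration TSH was also in range, and the alternative was non-response. Where the alternative is multiple imputation, the average shift is smaller, and cases in opposite arms offset each other in the difference. This is unlikely to decide the trial, but it is worth correcting because the correction leaves on-time participants untouched.

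**What to change.** In all four SAP 16.2 tables, count the Stabilization windows from the first day of Stabilization (SP Day 1 = last day of titration + 1):

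- Visit 6: SP Days 1 to 63 (nominal SP Day 42).
- Visit 7: after SP Day 63 (nominal SP Day 84).

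For on-time participants SP Day 63 is Day 126+63 = 189, 168+63 = 231, 210+63 = 273 and 252+63 = 315, so the current cut-offs are reproduced exactly.

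Also state that a scheduled Visit 6 TSH cannot serve as the end-of-Stabilization value, which covers a Visit 6 held more than 63 days into Stabilization, and state how participants are assigned to the four tables. An upper limit on the Visit 7 window would not help, because a misfiled Visit 6 lies at the early end of that window.

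The cost is a table edit and a new reference date in the visit derivation, with no new data. The downside is that a few participants would change from observed to missing at the end of Stabilization and then follow the SAP 10.1 rule.
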